7.3 Variables

7.3.1 Exposure

The primary exposure is treatment with ≥ 1 cycle of pembrolizumab. Treatment details will be extracted from structured data to derive relevant variables of interest, including but not limited to number of pembrolizumab cycles, treatment type (i.e., monotherapy or combined with PBC), pembrolizumab duration, year of first pembrolizumab administration,

PRODUCT: MK-3475	PROTOCOL/AMENDMENT VERSION NO.: 00-v03
REVOPS ID NO: NIS104408	NIR DRC APPROVAL DATE: 11/24/2025
EPIDEMIOLOGY NO.: EP05026.164	

chemotherapy name, chemotherapy duration, date of surgery, and radiation therapy type, if applicable and as available.

7.3.2 Outcomes

Health outcomes: Clinical events or outcomes which may be represented as diagnoses, treatment or procedures (examples include syncope, disease progression or hypoglycemia collected as study endpoints, or death). Any herein described health outcomes, collected per the protocol, will be summarized as part of any interim analysis (if required) and in the final study report.

The primary outcome of interest for the current study will be death, as measured by rwOS, defined as the time from pembrolizumab treatment start to date of death. rwOS is a validated endpoint to measure the effectiveness of advanced cancers, including NSCLC [Lasiter, L., et al 2022] [Curtis, M. D., et al 2018], and some early-stage cancers, such as breast cancer [Zhang, Q., et al 2021]; however, rwOS has not yet been validated for early-stage NSCLC. Patients without a date of death will be censored on the date of the last follow-up or data cutoff date (June 30, 2027), whichever occurs first. A composite mortality variable that already exists in the FHRDs will be used. This composite mortality variable represents a patient's vital status and date of death, combining publicly available Social Security Death Index (SSDI) data and obituary data (processed from obituaries, funeral homes and other sources) with the EHR-derived mortality data (i.e., structured date of death and abstracted information from available EHR documentation) [Curtis, M. D., et al 2018] [Zhang, Q., et al 2021]. Separate estimates of rwOS will be provided for each of the following: race, ethnicity, and age group.

In the eNSCLC FHRD, analyses of rwDFS and rwEFS as exploratory endpoints will be conducted for each of the following subgroups: race, ethnicity, and age group. The rwDFS endpoint assesses time from the date of a patient's surgery with evidence of complete resection to first instance of local recurrence, distant recurrence, progression, or death. rwEFS assesses the time from index date (i.e., pembrolizumab therapy start date) to first instance of local recurrence, distant recurrence, progression, or death. For both endpoints, patients without an event will be censored on the date of the last follow-up or data cutoff date (June 30, 2027), whichever occurs first. Both analyses will leverage composite variables derived from EHR data elements, although neither outcome has been validated in the eNSCLC FHRD.

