- Pembrolizumab, as a single agent, is indicated for the treatment of patients with metastatic non–small cell lung cancer (NSCLC) whose tumors express programmed death ligand 1 (PD-L1) [tumor proportion score (TPS) $\geq 1\%$] as determined by an FDA-approved test, with disease progression on or after platinum-containing chemotherapy. Patients with epidermal growth factor receptor (EGFR) or anaplastic lymphoma kinase (ALK) genomic tumor aberrations should have disease progression on FDA-approved therapy for these aberrations prior to receiving pembrolizumab [10/2015].
- Pembrolizumab, as a single agent, is indicated for adjuvant treatment following resection and platinum-based chemotherapy (PBC) for adult patients with stage IB (T2a ≥ 4 cm), II, or IIIA non–small cell lung cancer (NSCLC) [01/2023].

PRODUCT: MK-3475	PROTOCOL/AMENDMENT VERSION NO.: 00-v03
REVOPS ID NO: NIS104408	NIR DRC APPROVAL DATE: 11/24/2025
EPIDEMIOLOGY NO.: EP05026.164	

- Pembrolizumab is indicated for the treatment of patients with resectable (tumors ≥ 4 cm or node positive) non–small cell lung cancer (NSCLC) in combination with platinum-containing chemotherapy as neoadjuvant treatment, and then continued as a single agent as adjuvant treatment after surgery [10/2023].

The most recent FDA approval was for the neoadjuvant and adjuvant treatment of resectable NSCLC based on results from KEYNOTE-671. With this approval, FDA issued a post-marketing commitment (PMC) (4531-2) to “Conduct an integrated analysis from ongoing, completed, or planned clinical trials and other potential data sources as appropriate enrolling a sufficient representation of older adults ages 75 years and older, and United States (US) racial and ethnic minority patients that is reflective of the US population of patients with NSCLC, to further characterize the efficacy and safety of pembrolizumab in combination with platinum-containing chemotherapy and pembrolizumab as a single agent in these patients.”

To fulfill a portion of the FDA PMC, Sponsor is proposing to conduct a real-world post-authorization effectiveness study (PAES) to characterize the real-world effectiveness (overall survival) of pembrolizumab for the treatment of NSCLC among US patients across races, ethnicities, and age groups. This real-world study will complement an integrated analysis of clinical trial data.

PRODUCT: MK-3475	PROTOCOL/AMENDMENT VERSION NO.: 00-v03
REVOPS ID NO: NIS104408	NIR DRC APPROVAL DATE: 11/24/2025

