7.2 Setting

Adult patients diagnosed with NSCLC and treated with pembrolizumab (monotherapy or in combination with PBC) between October 2, 2015 (first FDA approval of pembrolizumab for NSCLC) and June 30, 2025 in the US will be eligible for inclusion in this study. Eligible patients will be identified from two Flatiron databases: the early non-small cell lung cancer (eNSCLC) Flatiron Health Research Database (FHRD) and advanced non-small cell lung cancer (aNSCLC) FHRD. Early-stage and advanced NSCLC patients will be analyzed separately. Details of each database are described in Section 7.4.

The follow-up time for each patient in this study spans from the start of patient activity in the database through the date of death (if any) or last confirmed activity date through June 30, 2027 (data cutoff). In the proposed study design, patients will have opportunity to accumulate ≥ 2 years of follow-up time for outcome ascertainment through June 30, 2027.

Inclusion criteria

- Diagnosis of NSCLC (any stage)
 - Patients initially diagnosed with early-stage NSCLC (Stage I-IIIA or IIIB with known surgical resection).
 - Patients initially diagnosed with advanced NSCLC (Stage IIIB- IV), or who were previously diagnosed with eNSCLC and subsequently developed recurrent or progressive disease.
- Age 18 years or older at the time of NSCLC diagnosis
- Received ≥ 1 cycle of pembrolizumab (monotherapy or in combination with PBC) for the treatment of NSCLC
 - Patients with evidence of treatment with pembrolizumab as monotherapy or in combination with PBC as neoadjuvant and/or adjuvant therapy for eNSCLC will be selected from the eNSCLC FHRD.

PRODUCT: MK-3475	PROTOCOL/AMENDMENT VERSION NO.: 00-v03
REVOPS ID NO: NIS 104408	NIR DRC APPROVAL DATE: 11/24/2025
EPIDEMIOLOGY NO.: EP05026.164	

- Patients with evidence of treatment of pembrolizumab as monotherapy or in combination with PBC as first-line therapy in the advanced setting will be selected from the aNSCLC FHRD.
- Pembrolizumab initiation date between October 2, 2015 and June 30, 2025 (to allow ≥ 2 years of follow-up time)
- Known (non-missing) race, ethnicity, or age (depending on the subgroup of interest)

Exclusion criteria

- Prior treatment with an IO agent or an investigational drug on or before initiation of pembrolizumab

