Real-world OS as defined in Section 7.3.2 will be estimated among patients using Kaplan-Meier methods. Median survival times and the probabilities of survival at key milestones of interest (e.g., 1-year, 5-year, etc.) and corresponding 95% confidence intervals (CI) will be calculated. Separate analyses will be conducted for each the following subgroups: Black or African American, Asian, other race, White, Hispanic/Latino, not Hispanic/Latino, elderly (≥ 75 years), and younger (<75 years). Racial subgroups with small sample sizes (<75 patients) may be combined with 'other race'. A descriptive summary of rwOS estimates will be provided for all races, ethnicities, and age groups. Given the descriptive nature of the study, no imputation for missing data or statistical testing will be performed. Sensitivity analyses may be conducted to evaluate the effectiveness of pembrolizumab among the subset of patients receiving pembrolizumab in line with currently approved indications (i.e., on-label use).

Exploratory analyses of rwDFS and rwEFS as defined in Section 7.3.2 will be conducted in the early-stage NSCLC population. The rwDFS endpoint will be evaluated among patients analyzed in Primary Objective 1 (i.e., surgically-resected patients who did not receive neoadjuvant therapy prior to surgery). The rwEFS endpoint will be evaluated among patients analyzed in Primary Objective 2 (i.e., resectable patients who received neoadjuvant therapy). For both outcomes Kaplan-Meier methods will be used to estimate median survival times and the probabilities of survival at key milestones of interest and corresponding 95% CI will be calculated. Separate analyses will be conducted for each race, ethnicity, and age group. Sensitivity analyses may be conducted to evaluate the effectiveness of pembrolizumab among the subset of patients receiving pembrolizumab in line with currently approved indications.

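### Exploratory rwDFS in the early-stage monotherapy cohort is timed from surgery, but patients enter only by later starting pembrolizumab, so the curve includes immortal time and is biased upward

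*Protocol*

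**What the plan says.** **Time origins (Protocol 7.3.2).** The rwDFS clock runs from the date of "surgery with evidence of complete resection to first instance of local recurrence, distant recurrence, progression, or death". The other two endpoints start at treatment. rwOS is "defined as the time from pembrolizumab treatment start to date of death", and for the third endpoint the text reads "rwEFS assesses the time from index date (i.e., pembrolizumab therapy start date".

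**Entry (7.2).** The exposure criterion is "Received ≥ 1 cycle of pembrolizumab (monotherapy or in combination with PBC) for the treatment of NSCLC". Early-stage patients are those with evidence of either regimen "as neoadjuvant and/or adjuvant therapy for eNSCLC will be selected from the eNSCLC FHRD".

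**Analysis population and estimator (7.8).** rwDFS is evaluated in the Objective 1 cohort (early-stage monotherapy), described as "surgically-resected patients who did not receive neoadjuvant therapy prior to surgery". rwEFS is evaluated in the Objective 2 cohort (early-stage combination), described as having received neoadjuvant therapy. On the estimator, the section states: "For both outcomes Kaplan-Meier methods will be used to estimate median survival times". It mentions no delayed entry or landmark.

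**Sequence of care (Section 5).** In the listed adjuvant indication, single-agent pembrolizumab "is indicated for adjuvant treatment following resection and platinum-based chemotherapy (PBC) for adult patients", so chemotherapy lies between surgery and the first dose.

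**Role of the endpoint (7.10).** rwDFS and rwEFS are offered to offset immature early-stage mortality data. The accompanying caution concerns lack of validation. Immortal time is not mentioned, although item 7.3 of the Annex 1 checklist, whose examples include time-related bias, is answered Yes with a reference to 7.10.

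**The concern.** A patient must survive from surgery to a first pembrolizumab cycle to be in the rwDFS analysis. Those who died in between are absent from the data, while those who got through bring the whole interval with them as event-free follow-up. The stated objective is effectiveness of pembrolizumab, so time before the drug was given, during which an event would have prevented entry, is credited to the drug.

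rwDFS is one of two endpoints meant to support interpretation where early-stage rwOS is immature. It is also the only one of the three endpoints that does not start at the index date, so it cannot be read on the same footing as the other two.

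A related inconsistency concerns who gets which endpoint. Section 7.2 allows neoadjuvant or adjuvant use under either regimen. Section 7.8 describes the monotherapy cohort as having no neoadjuvant therapy and the combination cohort as having had it. A neoadjuvant monotherapy patient and an adjuvant-only combination patient both satisfy 7.2, but neither fits the 7.8 description of their own cohort.

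**Working it through.** The protocol states no rwDFS median, rate or precision, so there is no figure to reproduce. Table 3 concerns median OS and is not an input. The check has a logical part and an illustration.

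**Logic**

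1. Origin: surgery (7.3.2).
2. Entry: at least one pembrolizumab cycle, given as neoadjuvant and/or adjuvant therapy (7.2).
3. rwDFS patients had no neoadjuvant therapy (7.8), so the first dose follows surgery in all of them.
4. Death between surgery and first dose makes entry impossible. The interval is strictly immortal for death.
5. No explicit rule excludes recurrence before the first dose. However, a patient who has recurred would ordinarily no longer be receiving adjuvant therapy, and 7.2 places recurrent disease under the advanced definition. The interval is therefore largely, but not strictly, immortal for recurrence.
6. Ordinary Kaplan-Meier from surgery counts everyone as at risk from time 0, so the curve stays near 100% until first doses begin.

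**Illustration (assumed values)**

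Take a constant hazard λ = ln 2 / M, with M the median DFS in months, and an event-free gap of g months forced by entry.

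- DFS from pembrolizumab start: S(t) = exp(−λt)
- Kaplan-Meier from surgery: exp(−λ(t − g)) for t > g

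The reported probability is too high by the factor exp(λg), and the median becomes M + g. Results at t = 12 months:

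| M (months) | From pembrolizumab start | From surgery, g = 2 | g = 4 | g = 5 |
|---|---|---|---|---|
| 36 | 79.4% | 82.5% (+3.1) | 85.7% (+6.4) | 87.4% (+8.0) |
| 48 | 84.1% | 86.6% (+2.5) | 89.1% (+5.0) | 90.4% (+6.3) |
| 60 | 87.1% | 89.1% (+2.0) | 91.2% (+4.1) | 92.2% (+5.2) |

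For M = 48 and g = 4: exp(−ln 2 × 12/48) = 84.1%, against exp(−ln 2 × 8/48) = 89.1%. At 24 months the same case moves from 70.7% to 74.9%. Over a wider range (gaps 1 to 6 months, medians 24 to 60 months) the 12-month excess is 1.0 to 13.4 points. It is upward in every case.

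A simulation of 400,000 patients with M = 36 and gaps varying around a mean of 5 months agrees: 87.3% from surgery and 79.3% from pembrolizumab start, against a true 79.4%.

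**Would delayed entry from surgery repair it?** Not in general. Nobody is at risk before the shortest gap g_min, so the estimator targets exp(−λ(t − g_min)). With M = 48 and t = 12:

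- all gaps equal to 4 months: exp(−ln 2 × 8/48) = 89.1%, the same as the uncorrected figure
- gaps from 3 to 5 months: exp(−ln 2 × 9/48) = 87.8%
- gaps from 1 to 7 months: exp(−ln 2 × 11/48) = 85.3%

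The target in each case is 84.1%. Delayed entry approaches it only if some patients start soon after surgery, and its early risk sets are then small.

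**Subgroups.** The inflation factor exp(λg) is the same in two groups only if λg is the same. With M = 36 in both groups but gaps of 2 and 5 months, the reported 12-month values would be 82.5% and 87.4%, a difference of 4.9 points with no true difference. This shows what unequal gaps would do. It does not show that they exist.

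**The case against.** **The endpoint is exploratory and untested.** It concerns one of four cohorts, there are no formal comparisons, and the protocol already asks for caution. This stands and limits the severity. It does not remove the defect, because the stated caution concerns validation and would not alert a reader to this bias.

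**Surgery is the conventional DFS origin, and a from-surgery curve in patients who went on to pembrolizumab is a legitimate description.** This stands if the curve is labelled as conditional on reaching the first dose. It is not so labelled, and the objective is effectiveness.

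**The separate analysis plan could deal with delayed entry.** It could, but the origin is fixed in the protocol, and delayed entry is a different estimand that need not remove the excess.

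**Stronger readings a reader might infer, which the protocol does not support:**

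- *Every adjuvant patient is affected.* An adjuvant combination patient falls in the Objective 2 cohort, where the endpoint is rwEFS from pembrolizumab start.
- *Anyone who recurred before the first dose is excluded.* No such rule is written. It is inferred from the adjuvant-setting requirement.
- *The bias is known to differ by age or race.* Section 5 says elderly patients tend to receive less intensive treatment. It says nothing about the surgery-to-pembrolizumab interval among those who did receive adjuvant pembrolizumab.
- *rwDFS would skip pre-surgical progression in neoadjuvant monotherapy patients.* On the 7.8 wording such patients are not in the rwDFS analysis. The mismatch with 7.2 leaves them without a clear endpoint, which is a different problem.

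**Conclusion.** The concern holds for rwDFS in the early-stage monotherapy cohort. Its existence and upward direction follow from the protocol's own origin, entry condition and estimator. They are strict for death and largely hold for recurrence. The size cannot be computed, because neither the gap nor the DFS hazard is given. Under constant hazards with medians of 36 to 60 months and gaps of 2 to 5 months, 1-year rwDFS is about 2 to 8 points too high and the median too long by the gap. A difference in bias between subgroups is possible if gaps or hazards differ, but it is not shown.

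Primary rwOS and the rwEFS origin are unaffected, so it would be wrong to infer that the primary objectives are compromised. This should be fixed before analysis, but it does not threaten the study's main results. The mismatch between the 7.2 and 7.8 cohort descriptions needs no assumption and should be settled in the same edit.

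**What to change.** 1. In 7.3.2, start rwDFS at pembrolizumab initiation, the index date of rwOS and rwEFS, in completely resected patients with no recurrence on or before that date.
2. Report the surgery-to-pembrolizumab interval by race, ethnicity and age group.
3. If a from-surgery curve is kept, label it as conditional on having reached pembrolizumab. Do not present delayed entry as an equivalent correction.
4. Reconcile 7.2 with 7.8 by assigning endpoints by sequence, not regimen: rwDFS where pembrolizumab began after resection, rwEFS where it began before. Remove the 7.8 parentheticals that redefine the Objective 1 and 2 cohorts.
5. Add a sentence on immortal time to 7.10, so that the Annex 1 checklist reference is correct.

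**Cost.** Wording in the protocol and the matching analysis plan. Pembrolizumab start is already the index date. Date of surgery is listed in 7.3.1 (as available), and recurrence dates are listed in the abstract. The downside is that rwDFS no longer uses the conventional from-surgery origin, which makes it less directly comparable with DFS reported from surgery elsewhere.

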7.3.3 Covariates

Covariates

Race and ethnicity are primary variables of interest. Racial groups will include White, Black or African American, Asian, and other (American Indian/Alaska Native, Native Hawaiian/Other Pacific Islander, multiple races, etc.). Individual racial groups will remain separate to the extent possible given sample size limitations. Any subgroup with <75 patients

PRODUCT: MK-3475	PROTOCOL/AMENDMENT VERSION NO.: 00-v03
REVOPS ID NO: NIS104408	NIR DRC APPROVAL DATE: 11/24/2025
EPIDEMIOLOGY NO.: EP05026.164	

will be combined into ‘other’. Final subgroup categories will be based on actual patient numbers at the time of data cut off. Ethnicity will be categorized as Not Hispanic/Latino or Hispanic/Latino.

Race and ethnicity information is collected as structured data in the EHR based on information collected from patients via intake interviews and forms, but exact processes may vary between oncology practices in the Flatiron Health Research Network (FHRN). Race categories with low representation in the US population (American Indian or Alaska Native, Native Hawaiian or Other Pacific Islander), and source data that contains a race description which falls in multiple race categories are included in ‘other race’. Source data whose race description states that patient declines to answer, or where it is otherwise unknown or uncoded is represented as NULL (i.e., missing) values. Patients missing race or ethnicity will be excluded from race- or ethnicity-specific analyses, respectively, but included in the age-specific analyses. Race data collected from the EHR in this manner has been used in peer-reviewed research on racial disparities in oncology [Maignan, K., et al 2022] [Tan, R., et al 2022] [Guadamuz, J. S., et al 2024].

Age is also a primary variable of interest. Patients will be categorized as elderly (≥ 75 years of age) or younger (< 75 years of age) based on age at initiation of pembrolizumab treatment.

Other Patient Characteristics for Descriptive Purposes

Other patient characteristics may be used to describe patients included in each analysis, including sex, ECOG performance status, smoking status, disease stage, histology, PD-L1 status, actionable genomic alteration status, treatment setting (e.g., adjuvant), and chemotherapy agents. The status of actionable genomic alterations sourced from the EHR is available in the aNSCLC FHRD (EGFR, ALK, KRAS, ROS1, BRAF, MET, RET, NTRK, HER2) and the eNSCLC FHRD (EGFR, ALK, HER2).

7.4 Data Sources

Two databases will be used to identify eligible patients: the eNSCLC FHRD and aNSCLC FHRD. Both FHRDs are longitudinal databases, comprising deidentified patient-level data, curated via technology-enabled abstraction. During the study period, the deidentified data are expected to originate from approximately 280 US cancer clinics (~800 sites of care). The majority of patients in the FHRDs originate from community oncology settings, with the remainder from academic medical centers.

The eNSCLC FHRD includes patients with an international classification of disease (ICD) code for lung cancer (ICD-9 162.x or ICD-10 C34x or C39.9) who visited a practice in the FHRN at least twice on or after January 1, 2019, and were included in a probabilistic sample of patients for abstraction to confirm a diagnosis of early (Stage I-IIIA) NSCLC with diagnosis date on or after January 1, 2019.

The aNSCLC FHRD includes patients with an ICD code for lung cancer (ICD-9 162.x or ICD-10 C34x or C39.9) who visited a practice in the FHRN at least twice on or after January

PRODUCT: MK-3475	PROTOCOL/AMENDMENT VERSION NO.: 00-v03
REVOPS ID NO: NIS104408	NIR DRC APPROVAL DATE: 11/24/2025
EPIDEMIOLOGY NO.: EP05026.164	

1, 2011, and were included in a probabilistic sample of patients for abstraction to confirm a diagnosis of advanced (Stage IIIB or higher) or recurrent NSCLC with diagnosis date on or after January 1, 2011.

Study data will be based on structured data and previously extracted data fields which will be sourced from EHR data. The exposures of interest, along with outcomes and other relevant variables will be assessed for reliability and validity.

A final dataset will be determined that meets the minimum data standards as set forth in Section 7.4.2 Feasibility Assessment and the following:

- Identification of the study population as set forth in Section 7.4.2 Feasibility Assessment
- Evaluation of the study exposures, outcomes, and covariates as set forth in Section 7.3 Variables

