7.10 Limitations of the Research Methods

Validity and interpretability of measurement:

- EHR-derived data are frequently collected for the purpose of the clinical management of oncology patients and not primarily for research purposes. The proposed study is subject to data that are available in the selected database and the level of granularity provided for available data.
- OS estimates may be biased due to possible misclassification of events resulting from incomplete or low sensitivity mortality data. However, the mortality data in the secondary data sources proposed for this study are enhanced by linking multiple data sources including data abstraction from EHR, SSDI, and obituaries, and the mortality variable used in the FHRDs has been shown to have high sensitivity (>90%) when compared to the National Death Index [Curtis, M. D., et al 2018] [Zhang, Q., et al 2021]. Validation of the mortality endpoint is one of the required criteria needed to select the data source used for the study.
- OS estimates may be biased due to uncontrolled confounding factors, including those that are available in the dataset (e.g., stage, treatment setting, year of diagnosis) and those that are not available in the dataset (e.g., age-related comorbidities). An exploratory analysis using propensity score weighting methods will attempt to balance confounders across subgroups using available covariates. It should be noted that the use of propensity score weighting may result in less precise effect estimates.
- Combining racial/ethnic minorities does not capture the heterogeneity that may exist within individual races or ethnicities. Individual racial groups will remain separate to the extent possible given sample size limitations.

Data completeness:

- As is common with observational studies utilizing real-world data, the main limitations for this study include lack of availability of data on certain variables and missingness in data obtained from the EHR. Certain variables may not be available with full completeness, such as race/ethnicity and treatment details.
- Additionally, patients may seek care outside of the supplier's network. This may contribute to missing, incomplete data and patient loss to follow-up.

PRODUCT: MK-3475	PROTOCOL/AMENDMENT VERSION NO.: 00-v03
REVOPS ID NO: NIS104408	NIR DRC APPROVAL DATE: 11/24/2025
EPIDEMIOLOGY NO.: EP05026.164	

Study design:

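### Neither database requires its two network visits to precede the first pembrolizumab dose, so plain Kaplan-Meier from that dose may overstate rwOS and rwEFS; separately, 7.2 and 7.3.2 give different starts of follow-up

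*Protocol*

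**What the plan says.** **Entry to the data (Protocol 7.4).** The early-stage database takes patients who "visited a practice in the FHRN at least twice on or after January 1, 2019" and who have a "diagnosis of early (Stage I-IIIA) NSCLC with diagnosis date on or after January 1, 2019". The advanced database takes patients "who visited a practice in the FHRN at least twice on or after January" 1, 2011. Neither rule mentions the first pembrolizumab dose. The eligibility list in 7.2 adds no ordering; its only timing condition on treatment is "Pembrolizumab initiation date between October 2, 2015 and June 30, 2025".

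**Time zero (Protocol 7.3.2).** rwOS is "defined as the time from pembrolizumab treatment start to date of death". rwEFS also runs from pembrolizumab start. One cycle is enough exposure (7.3.1), so very early deaths belong to the population being described.

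**Follow-up (Protocol 7.2).** "The follow-up time for each patient in this study spans from the start of patient activity in the database through the date of death" or the last confirmed activity up to the June 30, 2027 cutoff. This origin differs from the one in 7.3.2.

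**Estimator (Protocol 7.8).** Kaplan-Meier, unweighted for the primary objectives and weighted for the exploratory analysis in advanced disease. Late entry is not mentioned.

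**Limitations (Protocol 7.10).** It notes that "patients may seek care outside of the supplier's network", but only as a source of incomplete data and loss to follow-up. Left truncation and immortal time are not discussed, although item 7.3 of the ENCePP checklist, whose examples include time-related bias, is answered yes with a reference to 7.10.

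**The concern.** A two-visit rule guarantees that everyone in the data lived to the second visit. If that visit falls on or before the first dose, the guarantee covers time before time zero and does no harm. If it falls later, for example because the first cycle was given at the first network visit or treatment began elsewhere before transfer in, the interval from dose to visit is free of deaths by construction. Kaplan-Meier from the dose counts those patients as at risk during an interval in which they could not have been seen to die.

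The effect would be upward and strongest in the first months. It could reach all four primary rwOS analyses and rwEFS. If late entry is more common in some age, race or ethnic groups, it would also distort the descriptive contrasts that are the purpose of the study.

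The follow-up sentence in 7.2 raises a separate matter. For a patient whose database activity begins before pembrolizumab, follow-up reported on that definition would include time before index.

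**Working it through.** **Calendar floors.** In the early-stage database the diagnosis and visit windows open on the same day, January 1, 2019. In the advanced database the visit window opens in 2011, before the October 2015 treatment window. The calendar dates therefore add no truncation. Only the order of the second visit and the first dose matters.

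**Inputs**
- Planning median OS: 20 months (1.67 years), Protocol 7.5. Exponential survival is assumed, S0(t) = 2^(−t/20), with t in months.
- f: share of patients starting pembrolizumab whose second visit comes after the first dose. Not in the protocol; assumed.
- g: delay from first dose to that visit. Not in the protocol; assumed.
- Entry time is taken as independent of survival.

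**Formula.** A late entrant is observed only if alive at g, so the observed fraction is D = (1 − f) + f·S0(g). For t ≥ g, unadjusted Kaplan-Meier from first dose estimates S0(t)/D. Setting this to one half gives an observed median of 20 × (1 − log2 D), so the relative rise is −log2 D.

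**Worked case.** f = 30%, g = 3 months: S0(3) = 2^(−0.15) = 0.9013. D = 0.70 + 0.30 × 0.9013 = 0.9704. Median = 20 × 1.043 = 20.9 months. Six-month survival = 0.8123/0.9704 = 83.7%, against a true 81.2%.

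| f | g | D | Median, months | Rise | 6-month survival |
|---|---|---|---|---|---|
| 0% | any | 1 | 20.0 | 0% | 81.2% |
| 10% | 3 weeks | 0.9976 | 20.1 | 0.3% | 81.4% |
| 25% | 3 weeks | 0.9941 | 20.2 | 0.9% | 81.7% |
| 10% | 3 months | 0.9901 | 20.3 | 1.4% | 82.0% |
| 30% | 3 months | 0.9704 | 20.9 | 4.3% | 83.7% |
| 20% | 6 months | 0.9625 | 21.1 | 5.5% | 84.4% |

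A simulation of the three scenarios with delays of 3 or 6 months agreed to about 0.1 percentage point at six months. Letting each patient join the risk set at entry recovered 81.2% and 20.0 months.

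**Against the plan's own precision.** The narrowest interval in Table 3 (White, N = 10,000) is 1.62 to 1.72 years. It is reproduced by the exact exponential interval with 0.85 × 10,000/2 = 4,250 events. The 10%, 3-month case gives 1.67 × 1.014 = 1.69 years, inside it. The 30%, 3-month case gives 1.67 × 1.043 = 1.74 years, and the 20%, 6-month case 1.67 × 1.055 = 1.76 years, both outside. Table 2 lists 17,298 White patients in the advanced database before the split by treatment, so sampling error there could be small enough for such a shift to show.

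**Follow-up origin.** 7.2 counts from database activity and 7.3.2 from first dose. The two agree only when activity begins on the day of the first dose.

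**The case against.** **A reader might infer that all survival before the second visit is immortal, or that every primary estimate is biased upward.** The protocol supports neither. A patient with a consultation visit and then a dosing visit contributes no immortal time. The share affected is unknown and may be negligible.

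**The scenarios are assumptions.** If the first cycle is given at the first visit, a gap of weeks is the natural assumption, and 3 weeks moves the median by under 1% even with 25% affected. Gaps of months require treatment begun outside the network with that outside start date captured as index; 7.3.1 takes treatment details from structured data and does not say whether such dates are captured. One 20-month median also stands in for all four cohorts, although the protocol says that survival varies by stage, so the early-stage effect has not been sized. All of this stands, and it limits the claim about size.

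**A reader might infer that the 7.2 sentence causes the bias, or that the stated two years of follow-up is inflated.** Neither holds. 7.3.2 defines the rwOS clock without ambiguity, and the two-year statement is tied to the June 30, 2025 limit on pembrolizumab initiation. What remains is an inconsistency that would matter if follow-up were reported on the 7.2 definition.

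**Delayed entry may be in the statistical analysis plan.** 7.8 defers analytic detail to a separate plan that is not shown, so the absence of the rule here is not itself an error. That answer does not cover the conflict between 7.2 and 7.3.2, which is in the protocol text.

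**Delayed entry has its own assumption.** It is unbiased only if entry time is independent of survival, which referral or transfer patterns could upset. This stands and is the reason for the restricted check below.

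**Conclusion.** The concern holds conditionally. The two-visit rule, a clock at first dose and plain Kaplan-Meier together leave room for immortal time between the first dose and a later second visit. rwOS and rwEFS may be overstated to the extent that this happens, and not at all if both visits come first.

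At the 20-month exponential planning median, the assumed scenarios run from about +0.3% in the median (10% entering 3 weeks late) through +1.4% (10% at 3 months) to about +4% (30% at 3 months), with +5.5% for 20% at 6 months. These figures illustrate the possible size; they do not estimate what will occur, and they do not size the effect in early-stage disease.

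The conflict between 7.2 and 7.3.2 on the start of follow-up is definite and needs correcting whatever the statistical analysis plan says. Delayed entry is worth specifying because it changes nothing if nobody enters late and removes the bias if some do, provided entry time is independent of survival.

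**What to change.** - **7.2:** start follow-up at pembrolizumab initiation instead of at database activity.
- **7.3.2 and 7.8:** for rwOS and rwEFS, weighted and unweighted, let a patient enter the risk set at the later of pembrolizumab start and the second qualifying network visit, with time still measured from pembrolizumab start.
- **Reporting:** give the number of late entrants in each race, ethnicity and age group.
- **Check:** show the estimate restricted to patients whose second visit is on or before index. It contains no immortal time from this source and helps to judge the independence assumption, but it describes a selected group.

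The cost is wording plus one entry-time variable built from visit dates that the supplier already needs to apply its two-visit rule. Phase 2 of the feasibility assessment runs to April 2026, so the share and delay of late entrants could be measured before the analysis is fixed. The downsides are slightly wider early intervals, mainly in the smallest subgroups, and reliance on entry time being independent of survival.
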